6.0 SAFETY MONITORING

6.1 DEFINITIONS

Adverse Event

An adverse event is any untoward medical occurrence associated with the use of a drug in humans, whether considered drug related or not. It can be any unfavorable and unintended sign (e.g., an abnormal laboratory finding), symptom, or disease, temporally associated with the use of a drug whether it is related to the drug or not. This includes any newly occurring event, or a previous condition that has increased in severity or frequency.

Unexpected Adverse Event

An adverse event is considered unexpected if it is not listed in the investigator brochure or is not listed at the specificity or severity that has been observed in the event. “Unexpected” also refers to adverse events that are mentioned in the investigator brochure as occurring with a class of drugs or as anticipated from the pharmacological properties of the drug but are not specifically mentioned as occurring with the drug under investigation.

Serious Adverse Event

The terms “severe” and “serious” are not synonymous. Severity (or intensity) refers to the grade of an AE (see below). “Serious” is a regulatory definition and is based on subject or event outcome or action criteria usually associated with events that pose a threat to a subject’s life or functioning. Seriousness (not severity) serves as the guide for defining regulatory reporting obligations from the Sponsor to applicable regulatory authorities. A serious adverse event (SAE) is any adverse event, without regard to causality, that includes any of the following:

- Death
- A life-threatening adverse event (places the subject at an immediate risk of death)
- Inpatient hospitalization or prolongation of existing hospitalization
- A persistent or significant disability or incapacitation (substantial disruption of the ability to conduct normal life functions)
- A congenital anomaly or birth defect
- Is a **medically important event**. This refers to an AE that, in the medical judgment of the Principal Investigator, may jeopardize the subject, or may require medical or surgical intervention to prevent one of the outcomes listed above.

A planned medical or surgical procedure is not, it itself, an SAE.

6.1.1 Severity

The study site will grade the severity of adverse events experienced by study participants according to CTCAE version 5.0. Grade 1 and grade 2 adverse events do not require reporting in this study. The CTCAE displays Grades 1 through 5 with unique clinical descriptions of severity for each referenced AE. Should a subject experience any AE not listed in the CTCAE, the following grading system should be used to assess severity:

- Grade 1 (Mild AE) – experiences which are usually transient, requiring no special treatment, and not interfering with the subject’s daily activities
- Grade 2 (Moderate AE) – experiences which introduce some level of inconvenience or concern to the subject, and which may interfere with daily activities, but are usually ameliorated by simple therapeutic measures

- Grade 3 (Severe AE) – experiences which are unacceptable or intolerable, significantly interrupt the subject's usual daily activity, and require systemic drug therapy or other treatment
- Grade 4 (Life-threatening or disabling AE) – experiences which cause the subject to be in imminent danger of death
- Grade 5 (Death related to AE) – experiences which result in subject death

6.2 DOCUMENTING AND REPORTING OF ADVERSE AND SERIOUS ADVERSE EVENTS

The study will collect all Grade 3 and above adverse events, regardless of relationship to study therapy or study procedures, unless the event is one of the exceptions listed below. Severity grading will be based on CTCAE version 5.0. Grade 1 and 2 events will not be collected.

The following will NOT be collected as adverse events:

- An abnormal laboratory value will not be assessed as an AE unless that value leads to discontinuation or delay in treatment, dose modification, therapeutic intervention, or is considered by the investigator to be a clinically significant change from baseline. Any laboratory value meeting seriousness criteria must also be reported.
- Manifestations of chronic GVHD will not be collected as AE's unless they meet seriousness criteria.
- Hospitalization for elective treatment of a pre-existing condition that did not worsen from baseline is not considered an adverse event.

Non-serious, Grade 3 and above adverse events must be recorded in the database within 20 days of becoming aware of the event. Non-serious adverse events collected in the database will be compiled by the coordinating center and reported to the DSMB at regularly scheduled meetings.

Reporting procedures: All serious adverse events must be reported to Pfizer within 24 hours of first awareness of the event. If the event is fatal or life-threatening, it must be reported immediately. SAEs should be reported as soon as they are determined to meet the definition, even if complete information is not yet available. Sites must notify the coordinating center at Fred Hutchinson, and the study staff at Fred Hutchinson will prepare the report for Pfizer. Reports will be submitted on the Pfizer-provided *Investigator-Initiated Research Serious Adverse Event Report Form*, and faxed to Pfizer along with the *Reportable Event Fax Cover Sheet*. The Sponsor-Investigator at Fred Hutchinson will determine whether the event meets the criteria for expedited reporting, and will prepare the IND Safety Report as necessary. Significant and relevant follow-up information should also be reported to Pfizer as soon as

possible. Fred Hutchinson and the sites will assist Pfizer in investigating any SAE and will provide any follow-up information reasonably requested by Pfizer.

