- If a DSMB review is required because the stopping rule is triggered, patients who are already enrolled and taking glasdegib may continue treatment, pending the outcome of that review. Any enrolled patient who has consented but not started study drug may not start glasdegib treatment, pending the outcome of that review.
- The DSMB may, after review, recommend to stop the trial or continue it with or without modifications.

We will also include a stopping rule for grade ≥ 3 AEs that are known to be adverse reactions to glasdegib and hedgehog inhibitor pathway class drugs, such as musculoskeletal pain, muscle spasm, QT prolongation, anorexia, nausea, diarrhea, dizziness, elevated creatinine, elevated

transaminases, and tooth problems. If the lower bound of an 80% exact binomial confidence interval is > 20%, operationally given the total sample size 20, if any 2 of the first 4 or fewer subjects or any 3 of the first 7 or fewer subjects or any 4 of the first 11 or fewer subjects or any 5 of the 15 or fewer subjects or 6 of the first 20 or fewer subjects have unacceptable toxicity or Grade 3 or higher severity AEs, then enrollment will be halted while the DSMB reviews the study. If the true probability of Grade 3 or higher AE is 5%, the probability of study suspension under the above rule is approximately 0.02; if the true probability is 40%, the probability of suspension is approximately 0.85 (probabilities estimated from 5,000 simulations, using R version 3.5.0).

Since 2 of the first 4 patients experienced grade 3 muscle cramping, the stopping rule was triggered. Of note, these 2 patients had cramping prior to enrollment. The DSMB reviewed the data and allowed enrollment to continue but with an exclusion criterion for pre-enrollment grade 2 or 3 muscle cramps, or grade 1 cramps that occur at least weekly. For the purposes of the stopping rule, we will start again with subject #5, so if 2 of the next 4 or fewer, 3 of the next 7 or fewer, 4 of the next 10 or fewer, or 5 of the next 15 have unacceptable toxicity or grade 3 or higher severity AEs, then enrollment will be halted again while the DSMB reviews the study. If the true probability of Grade 3 or higher AE is 5%, the probability of study suspension under the above rule is approximately 0.02; if the true probability is 40%, the probability of suspension is approximately 0.85 (probabilities estimated from 5,000 simulations, using R version 3.5.0).

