Upper GI		 No symptoms	 Mild, occasional symptoms, with little reduction in oral intake during the past week	 Moderate, intermittent symptoms, with some reduction in oral intake, during the past week	 More severe or persistent symptoms throughout the day, with marked reduction in oral intake, on almost every day of the week
 Abnormality present but explained entirely by non-GVHD documented cause (specify): _____					

	0	1	2	3
Lower GI  Diarrhea	 No loose or liquid stools during the past week	 Occasional loose or liquid stools on some days during the past week	 Intermittent loose or liquid throughout the day, on almost every day of the past week, without requiring intervention to prevent or correct volume depletion	 Voluminous diarrhea on almost every day of the past week, requiring intervention to prevent or correct volume depletion
	 Abnormality present but explained entirely by non-GVHD documented cause (specify): _____			
Eye	 No symptoms	 Mild dry eye symptoms not affecting ADL (requiring eye drops ≤ 3 x per day)	 Moderate dry eye symptoms partially affecting ADL WITHOUT new vision impairment due to KCS Check all that apply  Requiring lubricant eye drops > 3 x per day  Punctal plugs	 Severe dry eye symptoms significantly affecting ADL Check all that apply  Special eyewear to relieve pain  Unable to work because of ocular symptoms  Loss of vision due to kerato-conjunctivitis sicca
	 Abnormality present but explained entirely by non-GVHD documented cause (specify): _____			

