Appendix 10. Patient-Reported Outcomes

FH8771: Glasdegib for Sclerotic Chronic Graft versus Host Disease

Glasdegib for Sclerotic Chronic GVHD

Response Assessment Patient Survey

Date of Visit: _____

Study Time Point: _____

Subject ID: _____

Subject Name: _____

Lee Symptom Scale

By circling one (1) number per line, please indicate how much you have been bothered by the following problems in the past 7 days:

		Not at all	Slightly	Moderately	Quite a bit	Extremely
SKIN:						
1.	Abnormal skin color.....	0	1	2	3	4
2.	Rashes.....	0	1	2	3	4
3.	Thickened skin.....	0	1	2	3	4
4.	Sores on skin.....	0	1	2	3	4
5.	Itchy skin.....	0	1	2	3	4
EYES AND MOUTH:		Not at all	Slightly	Moderately	Quite a bit	Extremely
6.	Dry eyes.....	0	1	2	3	4
7.	Need to use eye drops frequently..	0	1	2	3	4
8.	Difficulty seeing clearly.....	0	1	2	3	4
9.	Need to avoid certain foods due to mouth pain.....	0	1	2	3	4
10.	Ulcers in mouth.....	0	1	2	3	4
11.	Receiving nutrition from an intravenous line or feeding tube....	0	1	2	3	4
BREATHING:		Not at all	Slightly	Moderately	Quite a bit	Extremely
12.	Frequent cough.....	0	1	2	3	4
13.	Colored sputum.....	0	1	2	3	4
14.	Shortness of breath with exercise..	0	1	2	3	4
15.	Shortness of breath at rest.....	0	1	2	3	4
16.	Need to use oxygen.....	0	1	2	3	4
EATING AND DIGESTION:		Not at all	Slightly	Moderately	Quite a bit	Extremely
17.	Difficulty swallowing solid foods....	0	1	2	3	4
18.	Difficulty swallowing liquids.....	0	1	2	3	4

19. Vomiting.....	0	1	2	3	4
20. Weight loss.....	0	1	2	3	4
MUSCLES AND JOINTS:	Not at all	Slightly	Moderately	Quite a bit	Extremely
21. Joint and muscle aches.....	0	1	2	3	4
22. Limited joint movement.....	0	1	2	3	4
23. Muscle cramps.....	0	1	2	3	4
24. Weak muscles.....	0	1	2	3	4
ENERGY:	Not at all	Slightly	Moderately	Quite a bit	Extremely
25. Loss of energy.....	0	1	2	3	4
26. Need to sleep more/take naps....	0	1	2	3	4
27. Fevers.....	0	1	2	3	4
MENTAL AND EMOTIONAL:	Not at all	Slightly	Moderately	Quite a bit	Extremely
28. Depression.....	0	1	2	3	4
29. Anxiety.....	0	1	2	3	4
30. Difficulty sleeping.....	0	1	2	3	4

PROMIS-29 Profile v2.1

Please respond to each question or statement by marking one box per row.

Physical Function		Without any difficulty	With a little difficulty	With some difficulty	With much difficulty	Unable to do

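### Section 6.2 exempts non-serious chronic GVHD manifestations of any grade from AE collection, though several stopping-rule terms overlap with cGVHD features, so some grade 3+ events may go unrecorded

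*Combined protocol and SAP*

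**What the plan says.** Section 6.2 opens broadly: "The study will collect all Grade 3 and above adverse events, regardless of relationship to study therapy or study procedures". Among the listed exceptions it then says "Manifestations of chronic GVHD will not be collected as AE's unless they meet seriousness criteria". Section 6.1 makes clear that grade does not settle seriousness: "The terms “severe” and “serious” are not synonymous". A grade 3 event can therefore be non-serious and fall under the exception. Section 6.2 also says that the non-serious events sent to the DSMB are those collected in the database.

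The AE stopping rule in Section 3.12 covers grade 3+ events known as reactions to glasdegib or its class, "such as musculoskeletal pain, muscle spasm, QT prolongation, anorexia, nausea, diarrhea, dizziness, elevated creatinine, elevated" transaminases and tooth problems. After the rule was triggered, it restarts at subject 5 with boundaries of 2 in 4, 3 in 7, 4 in 10 and 5 in 15. The stated suspension probabilities are about 0.02 at a true rate of 5% and 0.85 at 40%.

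The primary endpoint (Section 5.5.2.1) is the type and severity of adverse events, together with cycles completed and reasons for discontinuation.

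**The concern.** The exemption acts at the point of collection. A site that regards a non-serious grade 3 event as cGVHD need not open an AE record, so the relationship question in Section 6.2.2 and Appendix 8 is never put. With no control arm, a misattribution cannot be corrected later by comparing rates.

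The exemption also sits uneasily with three other places. Section 6.1 counts worsening of an existing condition as an adverse event. Section 3.1.2 undertakes to characterize any treatment-emergent grade 3+ event. Section 6.2.2 has all AEs entered on the AE form.

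At stake are the completeness of the primary safety table and the operating characteristics of the stopping rule, whose stated probabilities refer to the true event rate and so presume that every qualifying event is counted.

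**Working it through.** **Overlap of terms.** Section 3.12 names ten event types. Set against the cGVHD instruments:

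| Stopping-rule term | Where it appears as a cGVHD feature |
|---|---|
| Diarrhea | Appendix 6, lower GI score 3: "Voluminous diarrhea on almost every day of the past week, requiring intervention to prevent or correct volume depletion" |
| Nausea, anorexia | Appendix 6, upper GI symptoms with reduced oral intake (nearest match) |
| Elevated transaminases | Appendix 7, ALT in the liver criterion |
| Musculoskeletal pain | Appendix 10, Lee scale item 21 (joint and muscle aches) |
| Muscle spasm | Appendix 10, Lee scale item 23 ("Muscle cramps") only |
| QT prolongation, dizziness, creatinine, tooth problems | No overlap shown |

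Six of the ten terms overlap to some degree, muscle spasm least clearly.

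**The plan's own figure.** Inputs: the restarted boundaries in Section 3.12 and 20 − 4 = 16 remaining patients (the last boundary is at 15, so the sixteenth does not alter the result). Let q be the probability that a patient has a counted event. The probability of having c events after k patients without suspension is

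f_k(c) = (1 − q) f_{k−1}(c) + q f_{k−1}(c − 1), for c below the boundary at k,

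with boundary 2 for k ≤ 4, 3 for k ≤ 7, 4 for k ≤ 10 and 5 for k ≤ 15. The suspension probability is 1 − Σ f_15(c).

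At q = 0.40:
- After 4 patients: f(0) = 0.6⁴ = 0.1296 and f(1) = 4 × 0.4 × 0.6³ = 0.3456. Still open: 0.4752.
- After 7: f(0), f(1), f(2) = 0.0280, 0.1306, 0.1866. Still open: 0.345.
- After 10: f(0) to f(3) = 0.0060, 0.0403, 0.1048, 0.1200. Still open: 0.271.
- After 15: 0.0060 × 0.9898 + 0.0403 × 0.9130 + 0.1048 × 0.6826 + 0.1200 × 0.3370 = 0.155, where the multipliers are P(Bin(5, 0.4) ≤ 4, 3, 2, 1).

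Suspension probability = 1 − 0.155 = 0.845, against the stated 0.85. At q = 0.05 the same recursion gives 0.016, against the stated 0.02. Both figures reproduce.

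**Sensitivity to non-collection.** If a share s of affected patients is not recorded, independently of everything else, the counted rate is q = p(1 − s). The documents give no value for s; the values below are assumptions.

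| Unrecorded share s | Counted rate, true 40% | Suspension | Counted rate, true 30% | Suspension |
|---|---|---|---|---|
| 0 | 0.40 | 0.845 | 0.30 | 0.606 |
| 10% | 0.36 | 0.765 | 0.27 | 0.515 |
| 25% | 0.30 | 0.606 | 0.225 | 0.373 |
| 50% | 0.20 | 0.297 | 0.15 | 0.163 |

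**The opposite error.** If disease-caused events had to count, the rule would trip more often. Suppose drug toxicity is 5% and, by assumption, a further 10% of patients have a listed event caused by cGVHD. The counted rate becomes 5% + 10% = 15%, and suspension rises from 0.016 to 0.163, about tenfold.

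**The case against.** Keeping manifestations of the underlying disease out of AE reporting and following them through response assessments is a deliberate and defensible choice. Several arguments support it here.

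- **Practice so far shows capture.** Grade 3 cramping in two of the first four patients was counted and tripped the rule. Section 3.12 adds "Of note, these 2 patients had cramping prior to enrollment", and a reader might infer that cramps are already being lost or reclassified as cGVHD. The text does not support that: nothing says those cramps were thought to be cGVHD, and they were counted.
- **Cramps are the weakest overlap.** Section 1.6.3.4 calls muscle spasm an on-target class effect, Appendix 8 treats a known drug response as pointing to relatedness, and neither the provider form nor the response table scores cramps.
- **A score is not an attribution.** The Appendix 6 form asks clinicians to score signs even when they are definitely not cGVHD.
- **There are backstops.** Serious events, including medically important ones, are still collected. The laboratory exception in Section 6.2 captures values that change treatment, need intervention or are judged clinically significant. Organ scores and ALT are recorded at visits, discontinuation reasons belong to the primary endpoint, and unacceptable toxicity is a separate trigger.
- **Omitting a true cGVHD flare is not bias.** The rule is aimed at drug reactions, and a patient with another recorded listed event still counts.

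These points rule out saying that such events never reach the database or cannot be recovered. They do not close the gap. No text feeds organ scores or symptom items into the AE tables or the stopping count. Unacceptable toxicity is undefined. The plan does not say which exception governs an ALT rise attributed to liver cGVHD. Nothing written ensures that later events will be handled as the first two were.

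**Conclusion.** The point holds as a possibility created by the text, not as a demonstrated loss. As written, a non-serious grade 3+ event attributed to cGVHD may bypass AE recording, relationship assessment, the DSMB and the primary safety table. The clearest exposure is for GI symptoms and musculoskeletal pain. It is less certain for transaminases and least clear for muscle spasm.

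For a given set of events, non-collection can only lower the count; by how much cannot be derived from the documents. A reader might take 0.297 as the rule's real sensitivity. It is not: it assumes that half of all affected patients go unrecorded, that losses are independent, and that every lost event is drug toxicity. Nor do the documents establish that the reported grade 3+ rates are biased downward, since that requires some omitted events to be drug-caused. This is a cheap improvement, best made prospectively because an event not entered is hard to reconstruct.

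**What to change.** Amend the Section 6.2 exception so that chronic GVHD manifestations are not collected as AEs unless they are serious or are grade 3+ events of a type named in the Section 3.12 AE stopping rule. Always collect the latter, with the baseline grade and the site's cGVHD attribution in separate fields. State that this provision prevails over the laboratory exception for transaminases. Give the DSMB the stopping-rule tally, and report the primary safety table, both with and without cGVHD-attributed events.

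Do not require every flagged event to count toward the trigger; the DSMB can judge from the two tallies. The cost is one amended sentence, two data fields, a few extra AE entries and a somewhat higher reported grade 3+ rate.

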3.12 DATA AND SAFETY MONITORING

This trial will be monitored in accordance with the Pfizer's Pharmacovigilance procedures. Adverse events, and SAEs will be reviewed internally as part of ongoing safety surveillance.

Monthly communications with the investigators and applicable site staff will be conducted to discuss study progress, obtain investigator feedback and exchange, and discuss "significant safety events" (i.e., AEs leading to dose reductions, related SAEs, and deaths).

In addition, an external DSMB will monitor the study every 6-12 months until the last patient has received 2 months of therapy, unless there are concerns that require ongoing monitoring.

While glasdegib has demonstrated safety, it has not been previously studied in cGVHD therapy after allogeneic hematopoietic cell transplantation. Current evidence suggests that mortality after initiation of cGVHD therapy may be as high as 20% at 56 days in some high-risk patient groups (Blood and Marrow Transplant Clinical Trial Network Protocol 0801). No interim analysis is planned during this trial, but there will be continuous monitoring for a stopping rule if an exact 1-sided 80% confidence interval for the true non-relapse mortality exceeds 10% -- for example, if 2 of first \leq 8, 3 of first \leq 15, 4 of first \leq 20 experience non-relapse mortality in the first 2 months. If the true probability of non-relapse mortality is 5%, the probability of study suspension under the above rule is approximately 0.08; if the true probability is 40%, the probability of suspension is approximately 0.99, estimated from 5,000 simulations, using R version 3.5.0.

Further details of the stopping rule include the following:

- Treatment-related mortality is any death occurring while receiving study drug, or within 30 days after discontinuation of study drug, that is possibly, probably or definitely related to the drug
- Relapse or progressive disease will factor into the attribution of cause but will not automatically prevent a death from being classified as treatment-related
- For purposes of this stopping rule, the count of patients (8, 15, etc) will reflect the order in which patients start treatment

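### The AE stopping rule counts non-serious grade 3+ events, but sites have 20 days to record them, so patients could start glasdegib after a boundary has been met

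*Combined protocol and SAP*

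**What the plan says.** **The rule.** Section 3.12 restarts the AE count at subject #5, with limits at 2 patients in up to 4, 3 in up to 7, 4 in up to 10 and 5 in 15. The action is taken when that many patients "have unacceptable toxicity or grade 3 or higher severity AEs, then enrollment will be halted again while the DSMB reviews the study". Seriousness is not a condition. The section records that the rule has already triggered once, on grade 3 muscle cramping in 2 of the first 4 patients.

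**The reporting clock.** Section 6.2 separates two classes of event. SAEs go out within 24 hours of awareness, through the coordinating center. For the rest: "Non-serious, Grade 3 and above adverse events must be recorded in the database within 20 days of becoming aware of the event". Their route onward is: "Non-serious adverse events collected in the database will be compiled by the coordinating center and reported to the DSMB at regularly scheduled meetings". Section 3.12 sets the meeting interval: "an external DSMB will monitor the study every 6-12 months until the last patient has received 2 months of therapy".

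**Other routes.** Section 3.12 also provides for internal review of AEs as ongoing surveillance, for AE reports to be received, reviewed and passed on by the coordinating-center PI, and for monthly communications with sites. The significant safety events listed for those communications are "AEs leading to dose reductions, related SAEs, and deaths".

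**Entry to treatment.** Section 3.0 requires the coordinating center to approve each participant before enrollment. Section 3.3.3 allows up to 28 days between consent and the start of study drug.

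**The concern.** A rule with a first boundary at 2 of 4 patients works only if the count is close to current when the next patient starts. Section 6.1 states that severity and seriousness are different things. A grade 3 muscle spasm or grade 3 nausea, both among the event types named for this rule, can therefore count toward a boundary without being an SAE. Such an event falls under the 20-day clock. If it is managed by holding the drug, which Sections 3.4.3 and 3.7 allow, it is not a listed item for the monthly call either.

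The event that completes a boundary could then be known at one center for up to 20 days while the other centers, following the protocol correctly, start new patients. What is at stake is the number of patients exposed between the crossing and the halt. In a trial of 20, with 16 from subject #5 onward, one such patient matters.

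**Working it through.** **1. The plan's own figures.** Inputs are the restarted limits (2/4, 3/7, 4/10, 5/15) and true event rates of 5% and 40%, all from Section 3.12. The method is an exact binomial recursion that checks the limit after every patient, with each outcome known at once.

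The first boundary can be checked by hand as P(2 or more of 4) = 1 − (1−p)^4 − 4p(1−p)^3:
- p = 0.05: 1 − 0.8145 − 0.1715 = 0.0140
- p = 0.40: 1 − 0.1296 − 0.3456 = 0.5248

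Carrying the recursion through all four limits over 15 patients gives 0.0158 and 0.8452, against the stated 0.02 and 0.85. The plan's figures reproduce. They are probabilities that a boundary is ever crossed, and a reporting delay does not enter them.

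**2. Does any passage give a faster clock?**

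| Route | Covers a non-serious grade 3 event managed by a hold? | Time limit |
|---|---|---|
| SAE report (6.2) | No | 24 hours |
| Database entry (6.2) | Yes | 20 days from awareness |
| Monthly call list (3.12) | Not listed | Monthly |
| Internal surveillance (3.12) | Yes, in general terms | None stated |
| Coordinating-center PI review (3.12) | Yes, in general terms | None stated |
| Participant approval (3.0) | No AE tally attached | Before enrollment |

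Continuous monitoring is stated for the mortality rule, not for the AE rule. The bar on consented patients starting drug is listed among the mortality rule's details, and it acts only once a trigger has been recognised. No section says who keeps the AE count or how often. The firm upper limit on delay is therefore 20 days from awareness.

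**3. Size of the delay.** Accrual is not stated, so rates of 0.5, 1 and 2 starts per month over all centers are assumed, with a 30.4-day month and starts arriving as a Poisson process.

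- Expected starts in the window = rate × days / 30.4
- P(at least one) = 1 − exp(−expected starts)

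| Starts per month | Expected, 20 days | P(at least one) | Expected, 24 hours |
|---|---|---|---|
| 0.5 | 0.5 × 20/30.4 = 0.33 | 28% | 0.5 × 1/30.4 = 0.02 |
| 1 | 1 × 20/30.4 = 0.66 | 48% | 1 × 1/30.4 = 0.03 |
| 2 | 2 × 20/30.4 = 1.32 | 73% | 2 × 1/30.4 = 0.07 |

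**4. Cross-check.** A simulation of the restarted rule used 16 patients, a true rate of 40%, onset uniform over 60 days and 2,000 runs per case. With a 20-day lag it gave mean extra starts of 0.29, 0.66 and 1.24, and chances of at least one of 25%, 48% and 69%. These agree with the formula, allowing for simulation error and for runs in which few patients are left to start.

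**The case against.** Twenty days is a limit for database entry and does not forbid earlier contact. Section 3.12 gives the coordinating-center PI responsibility for reviewing AE reports and for timely safety reporting, and it describes ongoing internal surveillance of AEs. The rule was in fact recognised at its first boundary, on the event type most in question. Accrual may be slow in a rare disease, and then the expected number of extra starts is well below one. All of this stands, and it limits the size of the point. It does not close the gap. None of these routes has a time limit, and the documents do not say how quickly the first trigger was recognised or whether anyone started drug in between.

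Two stronger readings are tempting, and the documents do not support either.

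- **That the halt waits for the next DSMB meeting.** A reader might multiply 1 to 2 starts per month by a 6-month interval and infer that 6 to 12 of the remaining 16 patients could start first. Section 3.12 places the halt before the DSMB review, and the compiled report in Section 6.2 is routine reporting that is not described as the trigger. The product also assumes that every crossing falls just after a meeting and that patients never run out. Even if nobody counted between 6-monthly meetings, the same simulation gives means of 3.3 and 5.3 extra starts at 1 and 2 per month. No such figure belongs in the finding.
- **That the stated suspension probabilities are too optimistic.** They reproduce and do not depend on the delay. The protocol states no expected number of patients exposed after a crossing, so no stated figure is contradicted.

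**Conclusion.** The mismatch is real but narrow. The AE rule counts grade 3+ events regardless of seriousness, while the only timed path for a non-serious event managed by a hold allows 20 days from awareness. Followed as written, the plan could let patients start drug after a boundary has been met.

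The size is up to roughly one extra patient: 0.33 to 1.32 expected starts across the assumed accrual range. This rests on the assumed rates, on Poisson starts and on the full 20 days being used, so it is an upper figure for the reporting delay at each rate. It excludes the time from first dose to onset and from onset to awareness, which faster notice would not remove. The point does not undermine the design. It is a cheap safety improvement that should be made.

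**What to change.** Amend Sections 6.2 and 3.12 as follows.

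1. Sites notify the coordinating center within 24 hours of awareness of any grade 3+ AE that counts toward the AE stopping rule. Full database entry can stay at 20 days.
2. The coordinating center is named as keeper of the tally and updates it on receipt of each notice.
3. The tally is checked at enrollment approval and again before each first dose, because first dose can follow consent by up to 28 days.
4. These events and toxicity-related holds are added to the monthly-call list.

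The cost is protocol wording, one short message per event and one tally check per new start. Sites already notify this center of SAEs and it already approves each participant, so no new staff or procedures are needed. The boundaries and the stated suspension probabilities stay as they are.
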